Steady state trough concentration (Ctrough) was reached by day 15 and exceeded 15μ g/ml at all dose levels. There was marked inter-patient variability in PK parameters resulting in substantial overlap between dose levels and trough concentrations did not appear dose-dependent. Patients received $1-22^+$ cycles

(median = 2). One patient each with hepatoblastoma or desmoplastic small round and all 5 who received therapy for a year or more had Ctrough $\ge 30 \,\mu\text{g/ml}$. All patients with evaluable DCE-MRI (n=8) experienced decreases in tumor blood volume and permeability (Ki; p<0.01). PIGF increased, whereas endoglin and soluble VEGFR2 decreased (p<0.01; n=31).⁴⁰

2.4.2 Pharmacology/Pharmacokinetics/Correlative Biological Studies

Hypertension was seen in several patients in the pediatric Phase I dose escalation study, which is a class effect seen with other VEGF blocking agents. Such hypertension has been treatable with anti-hypertensives and may ultimately be a biomarker of treatment effect. Pediatric specific guidelines for the management of VEGF blocking agent-induced hypertension have been developed for other COG Developmental Therapeutics studies (e.g. ADVL0413, ADVL0612, ADVL0714, and ADVL0815) and will be used for this trial. In the adult Phase I pazopanib trial, a relationship between steady-state trough concentrations and the occurrence of hypertension could be described by a logistic regression model. Twenty (77%) of the 26 patients with Ctrough values > 15 μ g/mL on Day 22 developed hypertension, versus 11 (39%) of the 28 patients who had lower Ctrough values.⁴² In the pediatric phase I trial, the mean Ctrough in patients with drug related hypertension (n=13) was 42±13 g/ml versus 29±13 g/ml in normotensive patients (n=27; p=0.008), suggesting a relationship between blood pressure elevation and drug exposure. In addition pediatric patients with a best response of stable disease had a 30% incidence of blood pressure elevation within the first two cycles, and 47% incidence over all cycles. This trial will seek to expand our understanding of the relationship of pazopanib Ctrough to hypertension, and the utility of hypertension as a pharmacodynamic or predictive marker.

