- 4.5.4 Concomitant administration of pazopanib with esomeprazole decreases the bioavailability of pazopanib by 40% (AUC and Cmax). Co-administration of pazopanib with Proton Pump Inhibitors (PPIs) should be avoided. Co-administration of pazopanib with PPIs is PROHIBITED from 24 hours before the first dose of pazopanib until after the final PK blood sample is collected on Day 15 ± 1 day of Cycle 1. After this, if the concomitant use of a proton-pump inhibitor (PPI) is medically necessary, it is recommended that the dose of pazopanib be taken without food once daily in the evening concomitantly with the PPI (Section 4.8). If the concomitant administration of an H2-receptor antagonist is medically necessary, pazopanib should be taken without food at least 2 hours before or at least 10 hours after a dose of an H2-receptor antagonist. Pazopanib should be administered at least 1 hour before or 2 hours after administration of short-acting antacids.
- 4.5.5 Concurrent Anti-Hypertensive Therapy: The algorithm in Section 5.4.1 will be used to grade and manage pazopanib related hypertension. Should initiation of anti-hypertensive therapy be required, single agent therapy (commonly including the calcium channel blockers amlodipine or nifedipine) may be started without notifying the study chair.

- 4.5.6 Anti-inflammatory and anti-platelet agents (e.g. aspirin, and/or ibuprofen, or other NSAIDs) could result in elevated blood pressure or increased bleeding episodes when co-administered with pazopanib and therefore should be used with caution.
- 4.5.7 Patients' medications should be reviewed at eligibility, before treatment initiation, and during treatment. Any concomitant medications that are "generally accepted" to cause a risk of Torsade de pointes are prohibited (see Appendix IIIB). Those "associated" with a risk of QTc prolongation and/or Torsades de pointes should be discontinued or replaced with drugs that do not carry these risks, if possible. Patients who must take these medications should be watched carefully for symptoms of QTc prolongation, such as syncope. Performing additional EKGs on patients who must take one or more of these medications is recommended but not required, at the investigator's discretion.

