9.3 Analysis Populations

The modified Intent-to-Treat (mITT) population is the primary analysis population. The mITT will consist of all patients who have received at least one dose of protocol therapy.

The Safety population will comprise all patients in the mITT population. The safety population will be used for the analysis of safety data.

The Per Protocol (PP) population is a subset of the mITT population who meet all eligibility criteria.

The Pharmacokinetic (PK) population will comprise all patients in the mITT population for whom a pharmacokinetic sample is obtained and analyzed. The Pharmacokinetic Extended Sampling (PKES) population will comprise all subjects in the Pharmacokinetic population who received powder suspension and have at least one non-predose sample collected and analyzed using the extended sampling schedule in Section 7.3.2. PK analysis summaries, figures and listings will be based on PK and PKES populations.

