# 12.2. Pharmacokinetic Analysis

The PK and PKES population will be used for listings and summaries. The PKES population will be used for the figures.

Pazopanib concentrations will be listed by dose and cohort. Summary tables for PK and PKES populations for pazopanib concentrations will be presented by cycle/day, dose, and cohort. Similar summary tables of pazopanib concentrations will be presented by cycle/day and dose combining data from all cohorts. The following summary statistics for pazopanib plasma concentrations will be calculated: n, median, minimum, maximum, arithmetic mean, CV% mean, standard deviation, geometric mean, CV% geometric mean.

Steady state trough plasma pazopanib concentrations will be determined for all subjects in the PK population. A concentration will be considered to be at steady state if the subject has taken 10 consecutive daily pazopanib doses without a dose reduction or interruption. A pre-dose concentration will be considered a trough sample if collected between 22-26 hours after the previous dose of pazopanib. Concentrations which are not at steady-state will be listed and flagged but excluded from summary tables for steady state concentrations. Similarly, concentrations which are not considered trough (blood sample taken after dosing or outside window 22-26 hours after previous dose) will be listed and flagged but excluded from summary tables.

The change in steady state trough plasma pazopanib concentrations will be characterized at the first cycle and each odd cycle after the first. The effect of cycle on change in steady-state plasma trough concentrations for each cohort will be assessed for each dose graphically by plotting median steady state trough concentrations against Cycle number.

If no substantial effect of the cycle is observed, steady-state trough concentrations will be combined for all sampling occasions and summarized by dose and cohort. Similar summary table will be presented by dose combining data from all cohorts.

A summary table summarizing pazopanib concentrations at each sampling occasion and a figure for pazopanib concentrations versus time by sampling occasion (Cycle 1 Day 1 and Cycle 1 Day 15) will be generated using PKES population combining data from all cohorts.

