#### 12.3.1. Statistical Analysis of Pharmacokinetic Parameters

All derived pharmacokinetic parameter values will be listed by dose, formulation, cycle/day, and cohort. PK parameters will be summarized by dose, formulation and cohort for both Cycle 1 Day 1 and Cycle 1 Day 15. PK parameters will also be summarized for both Cycle 1 Day 1 and Cycle 1 Day 15 combining data from all cohorts. For each of the PK parameters except Tmax, the following summary statistics will be calculated: n, median, minimum, maximum, arithmetic mean, CV% mean, standard deviation, geometric mean, CV% geometric mean. For Tmax, n, median, maximum and minimum will be calculated.

Steady state trough plasma pazopanib concentration values will be combined for all sampling occasions and summarized by age subgroups (28 days to <2 years, 2 to <12 years old, 12 to 18 years old) for each dose, cohort, and formulation unless a cycle effect on steady-steady trough concentration is identified. A similar analysis will combine data across all disease cohorts unless pharmacokinetic differences between the cohorts are observed.

PK parameters will be summarized by age subgroups (28 days to <2 years, 2 to <12 years old, 12 to 18 years old) for each dose, cohort and formulation. A similar analysis will combine PK parameters across all disease cohorts unless pharmacokinetic differences between the cohorts are observed.

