# 12.4. Assessment of pazopanib exposure from suspension formulation

Pazopanib exposures in subjects on the suspension formulation will be assessed by numerical comparison against exposures associated with efficacy in adult subjects. The proportion of subjects with steady state trough values above 20.5 (ug/mL), which is the efficacy threshold identified in subjects with advanced RCC (Shuttle et al 2014) will be calculated for each formulation, dose level, and cohort. A similar calculation will be presented combining subjects from all cohorts. If there is more than 1 steady state trough value for each subject, the first will be used.

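### SAP 12.2 and 12.3.1 pool repeated steady-state troughs without reducing them to one value per subject, after a by-eye cycle check on shrinking subsets that, read literally, leaves out tablet patients

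*SAP*

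**What the plan says.** - **Schedule.** Protocol 7.3.2 takes a pre-dose sample on Cycle 1 Day 15 and before each later odd-numbered cycle, with none required beyond Cycle 11. SAP 12.1 repeats this without the cap.
- **Valid troughs.** SAP 12.2 determines steady-state troughs for the whole PK population. A valid value is taken 22 to 26 hours after the previous dose and follows ten consecutive daily doses without reduction or interruption.
- **Cycle check.** For each cohort and dose, the effect of cycle is assessed by "plotting median steady state trough concentrations against Cycle number". What would count as substantial is not defined.
- **Pooling.** If the check is passed, "steady-state trough concentrations will be combined for all sampling occasions and summarized by dose and cohort", and then again with the cohorts combined. SAP 12.3.1 adds: "Steady state trough plasma pazopanib concentration values will be combined for all sampling occasions and summarized by age subgroups", unless a cycle effect has been identified. Protocol 9.11 summarises concentrations occasion by occasion, so pooling over occasions is an addition made in the SAP.
- **Contrast.** For the 20.5 µg/mL threshold, SAP 12.4 says: "If there is more than 1 steady state trough value for each subject, the first will be used".
- **Figures.** SAP 12.2: "The PKES population will be used for the figures". SAP 6.5 limits PKES to suspension patients with at least one post-dose sample from the extended schedule. Protocol 9.3: "PK analysis summaries, figures and listings will be based on PK and PKES populations".

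**The concern.** Patients leave treatment at very different times, so a table of pooled troughs gives most weight to those who stay. Its n looks like a number of patients but is a number of samples. SAP 9.2.11 describes the CV of PK parameters as between-subject, and a CV over pooled troughs would not be that.

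The safeguard is a plot whose points come from progressively smaller subsets of the starting patients. A movement in the median can be a change within patients or a change in who is left, and the plot cannot separate the two. If PKES governs the plot, a handful of suspension patients would also decide whether tablet troughs are pooled.

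PK characterisation is a secondary aim. SAP 12.3 derives AUC and Cmax only for the extended-sampling suspension patients, so troughs are the main exposure summary for tablet patients.

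**Working it through.** The PK sections state no sample size or precision, so there is no planned figure to reproduce.

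**1. Values per patient.** Cycle 1 Day 15 plus Cycles 3, 5, 7, 9 and 11 = 1 + 5 = 6 scheduled troughs. A patient reaches six within one dose group only if every sample is valid and the dose does not change.

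**2. Weight of long stayers.** Take ten patients, of whom L give six troughs and the rest give r each. The long stayers' share of values is 6L / (6L + r(10 − L)).
- L = 1, r = 2: 6/24 = 25%, against 10% of patients.
- L = 3, r = 1: 18/25 = 72%, against 30% of patients.

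**3. Number of values.** Assume a constant drop-out rate per cycle with median stay m. The share of patients still contributing at occasion k is 0.5^(2(k−1)/m). Phase I had a median of 2 cycles (Protocol 2.4.1); m = 2 and m = 4 are assumptions for this trial.
- m = 2: mean values per patient = 1 + 0.5 + 0.25 + 0.125 + 0.0625 + 0.031 = 1.97, so ten patients give about 20 values.
- m = 4: 1 + 0.707 + 0.5 + 0.354 + 0.25 + 0.177 = 2.99, so about 30 values.

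The design effect is 1 + (E[n²]/E[n] − 1) × ICC, with an assumed within-patient correlation (ICC) of 0.5 to 0.8. E[n²]/E[n] is 2.81 for m = 2 and 4.11 for m = 4.
- m = 2: 1 + 1.81 × 0.5 = 1.9, and 1 + 1.81 × 0.8 = 2.4.
- m = 4: 1 + 3.11 × 0.5 = 2.6, and 1 + 3.11 × 0.8 = 3.5.

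Dividing the values by these factors (19.7/2.4 = 8; 29.9/2.6 = 12), an n of 20 to 30 carries about as much information as 8 to 12 independent values.

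**4. What the plot shows under attrition.** Phase I troughs in Protocol 2.4.2 (read as µg/mL) were 42 in 13 hypertensive and 29 in 27 normotensive patients, each ±13. The overall mean is (13 × 42 + 27 × 29)/40 = 33.2. A simulation used mean 33.2, SD 13, m = 2 and, except in the last row, an assumed correlation of 0.3 between trough and time on treatment.

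| | C1D15 | C3 | C5 | C7 | C9 | C11 |
|---|---|---|---|---|---|---|
| Patients contributing | 100% | 50% | 25% | 12% | 6% | 3% |
| Median, no patient changes | 33.3 | 36.3 | 38.1 | 39.5 | 40.8 | 41.7 |
| Median, every patient falls 5% per occasion | 33.3 | 34.4 | 34.4 | 33.9 | 33.2 | 32.3 |
| Same fall, trough unrelated to stay | 33.2 | 31.6 | 30.0 | 28.5 | 27.1 | 25.7 |

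The second row would suggest a cycle effect where there is none. In the third row each patient falls by 1 − 0.95^5 = 23% by the sixth occasion, yet the plot is nearly flat and would permit pooling. With m = 4 the corresponding end points are 33.2 to 38.9 and 33.2 to 30.1.

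**5. Population of the plot.** Read together, SAP 12.2 (figures use PKES) and SAP 6.5 (PKES is suspension only) leave no tablet patient in the trough-by-cycle figure. SAP 12.1 stops extended sampling at six PK-evaluable patients, so the group would be about six, spread over up to seven cohorts. That does not fit the wording in SAP 12.2 that covers all PK-population subjects and plots each cohort and dose, and it departs from Protocol 9.3.

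**The case against.** - **Pooling is conditional.** True, and it limits the harm. A reader might infer that the pooled mean will be 13% to 16% too high. That follows from a constructed case: eight of ten patients at 25 µg/mL give one or two troughs (11 in all) and two at 40 give six each, so the geometric mean is 31.9 over 23 values against 27.5 over ten subjects. With 29 and 42 in place of 25 and 40 it is 35.2 against 31.2. But in that case the plotted median rises from 25 to 40, so the SAP's own condition would probably stop the pooling. When the medians are flat, the pooled median must lie between them. This does not cover n, CV% or a within-patient fall hidden by attrition.
- **Unpooled results are planned, and nothing is tested.** SAP 12.2 keeps tables by cycle and day, and SAP 8.4 tests no hypothesis. No standard error or interval is listed. The overstated n is therefore a matter of labelling and reading, not of a wrong inference.
- **The direction of bias is unproven.** Protocol 2.4.1 reports that "all 5 who received therapy for a year or more had Ctrough" of at least 30 µg/mL. A reader might infer that pooling inflates exposure. Taking the phase I figures as normal with SD 13, about 58% of all patients would exceed 30, and 0.58^5 is about 0.07, so five of five is weak evidence. Hypertension rules can also lead to holding, dose reduction or removal, so highly exposed patients may leave or change dose group.
- **The figure rule may be loose drafting.** Plausible: the last paragraph of SAP 12.2 assigns PKES to the concentration-time figure separately. The text still needs one correcting sentence.

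**Conclusion.** The point holds as a flaw in descriptive secondary outputs. It has three parts: pooled troughs are weighted by time on treatment (one to six values per patient), the pooling decision rests on medians that confound attrition with within-patient change, and the figure rule conflicts with the rest of SAP 12.2 and with Protocol 9.3. The count of six comes from the protocol schedule. The retention, correlation and ICC values above are assumptions, and the size and direction of any bias in this trial are not known.

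Three further inferences are not supported:
- That the comparison with adult efficacious exposure is affected. SAP 12.4 uses each subject's first trough.
- That the plot could never detect a cycle effect. Without selection, a 5% fall per occasion shows clearly (33.2 to 25.7). The fair statement is that the plot is unreliable when leaving treatment is related to exposure.
- That proton pump inhibitor use after Cycle 1 Day 15 (Protocol 4.5.4) calls for excluding later troughs. That is a separate matter, and the documents give no frequency of use.

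**What to change.** In SAP 12.2 and 12.3.1, or through the RAP addendum that SAP 8 provides for:

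- (a) Summarise one value per subject per dose level and formulation: the first steady-state trough, as in SAP 12.4, or the subject's geometric mean over occasions. Report n as subjects.
- (b) Assess the cycle effect by the ratio of each later trough to the same subject's Cycle 1 Day 15 trough at the same dose. Show the number of subjects behind each ratio and state what would count as substantial.
- (c) State that trough-by-cycle plots use the PK population and that only extended-profile plots use PKES.

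The cost is a SAP wording change, minor programming and a smaller stated n. Subjects without a valid Cycle 1 Day 15 trough drop out of (b). No new data are needed, and later troughs remain visible in the by-cycle tables. A listing flag for troughs taken on a proton pump inhibitor would be optional.

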# 12.3. Pharmacokinetic parameters

The following pharmacokinetic parameters will be determined from the plasma concentrationtime data for pazopanib from subjects who received pazopanib suspension and had extended pharmacokinetic sampling (Table 6).

AUC0-24	The AUC from time zero to 24 hours post dose (ng*hr*mL-1) (Day 15 only)
AUClast	The AUC from time zero to the last measurable plasma concentration sampling time (tlast) (ng*hr*mL-1) (Day 1 and Day 15
Cmax	The maximum (peak) observed plasma concentration following a single dose administration (ng/mL)
Tmax	The time to reach maximum (peak) plasma concentration following a single dose administration (hr)

#### Table 6Non-compartmental PK parameters for pazopanib

The pharmacokinetic parameters will be calculated by standard non-compartmental analysis according to the Sponsor's current working practices and using WinNonlin version 6.3 or higher. The analysis to assess pazopanib pharmacokinetics after administration of the suspension prior to continuing enrollment on the suspension cohort may be performed using

scheduled time. All calculations of non-compartmental parameters for the final analysis will be based on actual sampling times.

#### 12.3.1. Statistical Analysis of Pharmacokinetic Parameters

All derived pharmacokinetic parameter values will be listed by dose, formulation, cycle/day, and cohort. PK parameters will be summarized by dose, formulation and cohort for both Cycle 1 Day 1 and Cycle 1 Day 15. PK parameters will also be summarized for both Cycle 1 Day 1 and Cycle 1 Day 15 combining data from all cohorts. For each of the PK parameters except Tmax, the following summary statistics will be calculated: n, median, minimum, maximum, arithmetic mean, CV% mean, standard deviation, geometric mean, CV% geometric mean. For Tmax, n, median, maximum and minimum will be calculated.

Steady state trough plasma pazopanib concentration values will be combined for all sampling occasions and summarized by age subgroups (28 days to <2 years, 2 to <12 years old, 12 to 18 years old) for each dose, cohort, and formulation unless a cycle effect on steady-steady trough concentration is identified. A similar analysis will combine data across all disease cohorts unless pharmacokinetic differences between the cohorts are observed.

PK parameters will be summarized by age subgroups (28 days to <2 years, 2 to <12 years old, 12 to 18 years old) for each dose, cohort and formulation. A similar analysis will combine PK parameters across all disease cohorts unless pharmacokinetic differences between the cohorts are observed.

# 12.4. Assessment of pazopanib exposure from suspension formulation

Pazopanib exposures in subjects on the suspension formulation will be assessed by numerical comparison against exposures associated with efficacy in adult subjects. The proportion of subjects with steady state trough values above 20.5 (ug/mL), which is the efficacy threshold identified in subjects with advanced RCC (Shuttle et al 2014) will be calculated for each formulation, dose level, and cohort. A similar calculation will be presented combining subjects from all cohorts. If there is more than 1 steady state trough value for each subject, the first will be used.

# 12.5. Exploration of pharmacokinetic and pharmacodynamic relationship

Pazopanib PK/PD relationship will be explored between pazopanib steady state exposure (trough concentration) and biomarkers (angiogenic cytokines), efficacy (clinical benefits) or safety (drug related grade 2 and above hypertension). The analysis of the correlation of PK and biomarker will be described in a separate analysis plan. The proportion of subjects with steady state trough concentration above 20.5 ug/mL will be summarized for those with clinical benefits and those who do not have any clinical benefits. The steady state trough concentration will also be summarized by drug-related grade 2 and above hypertension.

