9.12 Analysis of Biological and Correlative Endpoints

The secondary analyses for examining the biologic relationship between tumor response and angiogenic cytokines as well as the effects on toxicity (including hypertension) of pharmacokinetic parameters (secondary objectives 1.2.7 and 1.2.9) will be conducted For the response outcome measure, patients will be classified as responders or non-responders according to paragraphs 2 and 3 of the **Primary Endpoint** (Section 9.8.1) above. If response occurs in 10% or more of patients, the following logistic model will be fitted:

The initial analysis will be carried out with the Day 15 trough plasma concentration.

Toxicities, which occur in a frequency of 10% or more of toxicity evaluable courses, will be analyzed for association between the risk of toxicity and the particular biological parameter. The data will be presented as a cross tabulation of the presence of frequency of the toxicity of interest in toxicity-evaluable cycles

accounting for possible patient frailty will be fitted to the data. This analysis will not be segregated by disease type.

The precision attendant with these analyses will depend on the overall frequency of response and toxicity amongst patients enrolled on the study. The precision observed will be quantified by 95% confidence intervals. Adjustment for multiple testing will not be used for these secondary objectives.

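### SAP 12.5 relates trough to clinical benefit only through an adult cut of 20.5 µg/mL; it should also summarise the trough itself by benefit and say what becomes of the Protocol 9.12 response model

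*SAP*

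**What the plan says.** Protocol aim 1.2.10 is to explore how pazopanib pharmacokinetics relate to biomarkers and to clinical outcomes, hypertension among them. The objectives table in SAP 2 keeps the clinical-outcome part in this SAP and sends only the biomarker part elsewhere. SAP 12.5 says the same: "The analysis of the correlation of PK and biomarker will be described in a separate analysis plan".

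For efficacy, SAP 12.5 then gives one summary: "The proportion of subjects with steady state trough concentration above 20.5 ug/mL will be summarized for those with clinical benefits", compared with those who have none. SAP 12.4 gives the origin of 20.5 µg/mL, "which is the efficacy threshold identified in subjects with advanced RCC", and there also settles repeated values: "If there is more than 1 steady state trough value for each subject, the first will be used". SAP 12.5 does not repeat that rule. For safety, the treatment is different: "The steady state trough concentration will also be summarized by drug-related grade 2 and above hypertension".

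Protocol 9.12 has a further analysis. "For the response outcome measure, patients will be classified as responders or non-responders", and "If response occurs in 10% or more of patients, the following logistic model will be fitted". The equation is not shown in the text available. The section goes on: "The initial analysis will be carried out with the Day 15 trough plasma concentration". Protocol 9.7.3 asks that departures from the protocol's analyses be recorded in the SAP (the RAP, in its terms) and in the final report. The SAP contains no such model and does not mention leaving it out.

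**The concern.** A yes/no cut treats a child at 21 µg/mL and a child at 45 µg/mL alike. If most children lie above it, the comparison rests on the few below. The only paediatric trough figures in the documents suggest that this will be so. Protocol 2.4.1 also reports that all five Phase I patients treated for a year or more had troughs of at least 30 µg/mL. That is the documents' own hint of a link between exposure and lasting benefit, and it lies well above the cut.

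The same paragraph summarises the trough directly by hypertension, so nothing in the data forces the coarser treatment for benefit. At stake is the efficacy half of aim 1.2.10: a similar proportion in the two groups would say little about whether exposure matters, and the SAP plans no other look at that question.

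**Working it through.** **Inputs.** Cut: 20.5 µg/mL (SAP 12.4). Phase I troughs (Protocol 2.4.2): 42±13 with drug-related hypertension, n=13; 29±13 in normotensive patients, n=27; reported p=0.008. The unit is printed as g/ml and is read here as µg/mL. Planned minimum enrolment: 77 (Protocol 9.1).

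**1. Reproduce the reported p-value, to settle whether ±13 is an SD.**
- As an SD: t = (42−29)/[13·√(1/13+1/27)] = 13/(13×0.3376) = 2.96, giving p=0.005 (pooled) or 0.007 (Welch). Rounding of the printed values allows about 0.003 to 0.015, so 0.008 fits.
- As a standard error: p=0.54, which does not fit. So 13 is the SD.

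**2. Combined Phase I distribution.**
- Mean = (13×42+27×29)/40 = 33.2.
- Variance = [38×13² + 13×(42−33.2)² + 27×(29−33.2)²]/39, with the unrounded mean 33.225; SD = 14.2.

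**3. Share above 20.5, normal shape.**
- Hypertensive: z = (20.5−42)/13 = −1.65, share 95.1%.
- Normotensive: z = (20.5−29)/13 = −0.65, share 74.3%.
- Weighted: (13×0.951+27×0.743)/40 = 0.81. One normal curve with mean 33.2 and SD 14.2 also gives 81%.

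**4. Information kept by the cut.** For a normal trough X and log-odds of benefit linear in X, this is the squared correlation of X with the indicator X>20.5, that is φ(z)²/[p(1−p)]. With z = (20.5−33.2)/14.2 = −0.89 and p = 0.814, it is 0.473, so about 53% is lost. Put another way, 77 patients on the cut are worth about 77×0.473 = 36 on the trough itself.

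**5. Sensitivity.**

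| Assumption | Share above cut | Information lost |
|---|---|---|
| Normal, or two-group normal mixture | 81% | 53% |
| Lognormal, relation linear in log trough | 83% | 55% |
| Lognormal, relation linear in trough | 83% | 73% |
| Lognormal mixture, log / raw scale | 81% | 48% / 67% |
| Normal, other shares | 50% / 70% / 75% / 90% | 36% / 42% / 46% / 66% |

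Under a normal shape the loss passes one half only when at least about 79% lie above the cut. Redrawing samples of 40 from the fitted normal gives a share of 71–91% and a loss of 43–67%; about 69% of draws exceed one half.

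**6. Illustration of the loss.** Suppose groups of 13 and 27 with and without benefit differed by 13 µg/mL, SD 13. These are the Phase I hypertension figures, borrowed only for scale. The proportions above 20.5 would be 95% and 74%. A t test on the trough would have about 81% power. Comparing proportions would have about 21% with Fisher's exact test and 31% with the less conservative Boschloo or Barnard test.

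**The case against.** Much can be said for the SAP.

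- **A threshold question is legitimate.** The protocol's pharmacology is threshold-like: little receptor inhibition below 18 µg/mL (Protocol 2.2.3), and effects above 15 (2.3) or 15–20 µg/mL (2.3.1). If benefit truly steps up near 20.5, the cut loses little. This stands, and is why the proportion should be kept. But no document shows such a step for benefit in children.
- **The analysis is exploratory.** SAP 8.4 plans no hypothesis tests, and individual concentrations are listed (SAP 12.2), so the data are not lost. This stands, and limits the weight of the point.
- **Phase I may not carry over.** It mixed tablet doses of 275–600 mg/m² with suspension (Protocol 2.4.1). This stands; hence the range.

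A reader might infer that the SAP replaces the protocol's model with the cut. The documents do not support that. The Protocol 9.12 model concerns objective response, while SAP 12.5 uses clinical benefit, which includes stable disease (SAP 10.2). The model applies only if at least 10% respond, and SAP 4.3 says the study was declared futile on benefit-risk after stage 1, so it may never be triggered. Its equation is not visible, and SAP 1 sends pharmacodynamic and biomarker detail to a separate plan that might hold it. What can be said is that this SAP omits the model without saying so.

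A reader might also infer that the two benefit groups must look alike whatever the truth. Step 6 contradicts this: 95% against 74% is a visible gap of about 21 points.

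**Conclusion.** The point holds in a limited form. SAP 12.5 relates trough to clinical benefit only through an adult threshold, while summarising the trough itself by hypertension; and the SAP neither carries the conditional Protocol 9.12 response model nor records its omission.

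If the Phase I troughs carry over, about 81% of children exceed the cut. If the relation is also roughly linear, about half of the information is discarded, with 43–67% from sampling error alone. That more than half is lost should not be stated as a fact: it is the central estimate under these assumptions, it does not follow from most children being above the cut, and it would not hold under a true threshold near 20.5. The power figures in step 6 illustrate the loss and do not describe a planned test. The consequence is confined to an exploratory, descriptive analysis for secondary aim 1.2.10; the objective response result and the two-stage decision rule are untouched.

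**What to change.** Add to SAP 12.5: 

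- The first steady-state trough per subject (usually Cycle 1 Day 15) will be summarised with n, median, range, geometric mean and CV%, and plotted, for subjects with and without clinical benefit.
- The proportion above 20.5 µg/mL will be kept as a supplement.
- The Protocol 9.12 logistic model for objective response, starting with the Day 15 trough, will be fitted if 10% or more of patients respond. If it has been dropped, or moved to the separate plan, say so and give the reason; a dropped model should be recorded as a deviation under Protocol 9.7.3.

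The cost is one more table and one figure from troughs already collected, plus a sentence on the model.
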